2.2 Primary Study Endpoint

The primary endpoint of this study is evidence of injury to the artery or cerebral ischemia secondary to shunt placement and removal.

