4 SUBJECT POPULATION

4.1 Inclusion Criteria

Subjects will be included in this study if they meet all of the following inclusion criteria:

1. Between the ages of 18-80 years old
2. Have undergone carotid endarterectomy with any Integra Sundt™ carotid shunt before the date of study initiation
3. Availability of records on post-operative imaging of the carotid artery either by carotid duplex ultrasound or angiogram

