5 STUDY PROCEDURES

This study is a retrospective review of patients who have undergone a carotid endarterectomy procedure with the use of the Sundt™ carotid shunt prior to study initiation.

Eligible subjects for the study should be identified by the 3-digit site number followed by the 3-digit subject ID. Numbering of the subjects should be done in a reverse chronological order with the most recent subject being 001 followed by the second most recent being 002 and so forth.

Required information will be collected through a review of the patient chart or electronic medical records (EMR) by the Principal Investigator or delegated personnel. The delegated staff

member shall collect demographics, details surrounding the procedure, and the post-operative assessment.

- **Demographics**
 - Age
 - Gender
 - Height
 - Weight
 - Relevant Past Medical History
 - Transient Ischemic Attack (TIA)
 - Stroke
 - Asymptomatic Carotid Stenosis
 - Bleeding Disorder
 - Diabetes
 - Smoking
 - Other relevant past medical history per the investigator's opinion
 - Past Surgical History
 - Previous Head or Neck Surgery
 - Previous Head or Neck Radiation
 - Previous Vascular Surgery
 - Other relevant surgical history per the investigator's opinion
 - Diagnosis / Indication for Surgery
 - Medications
- **Procedure**
 - Date of surgery
 - Procedure(s) performed
 - Duration of surgery
 - Device information, including lot number
 - Medications
 - Any complications noted in the operative report and in the investigator's opinion determined to be related to the device
- **Post-operative Assessment (up to 60 days post-procedure)**
 - Evidence of cerebral ischemia as indicated by post-operative neurological exam
 - Evidence of injury to artery as seen on post-operative imaging of the carotid artery either by carotid duplex ultrasound or angiogram

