5.1 Device Performance

The delegated site staff will collect information regarding the device performance.

The following device performance questions will be part of the case report form and will be collected from the patient medical record including both the operative note and the anesthesia record for the procedure. For the “yes / no” questions below, if the medical record is silent on the answer to the question it will be assumed that the answer is “no”.

1. Was the shunt use routine or selective? If selective, specify the test and the result that led to use of the shunt.
2. Was there any delay in surgery or complication due to preparation of the device for surgery? If yes, please explain.
3. What was the clamping method type for shunt insertion?
4. How long was the carotid artery cross clamped for shunt insertion?
5. Was there any device-related damage to the artery during insertion of the shunt? If yes, please explain.
6. Was there evidence of clot formation within the shunt at any point during the procedure? If yes, describe how this was detected and what was the remedy. What was the impact to the procedure?
7. Was there any evidence of reduced flow within the shunt other than clot formation (e.g. due to kinking, malposition within the artery)?
8. Was there any evidence of excessive bleeding around the shunt after initial placement? If yes, what was the remedy and the result of that remedy?
9. Did removal of the shunt cause vessel injury or complicate closure? If yes, please explain.
10. Was there evidence of post-operative cerebral ischemia noted in the neurological exam?
11. Did the subject experience injury to the artery due to the device as evidenced by the imaging of the carotid artery either by carotid duplex ultrasound or angiogram?
12. Were there any other device-related complications not previously recorded in the case report forms? If yes, please explain.

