6 STATISTICAL ANALYSIS

The PMCF is a retrospective chart review. All analyses will be descriptive in nature. No formal statistical analyses will be performed. The study objectives will be presented by summary statistics.

Summary statistics (mean, standard deviation, quintiles, counts, and percentages) will be presented for all demographic (i.e. age, gender, etc.), clinical baseline characteristics (diagnosis, medical history, medications), surgical procedures (procedures performed, duration of surgery) and complications.

The primary objective will be evaluated by summarizing the incidence of injury to the artery or cerebral ischemia secondary to shunt placement.

All statistical analysis will be conducted using SAS.

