7.2.6. Post-operative Assessment (up to 60 days post-procedure)

Post-operative assessment will be summarized, details will be listed by subject.

- Evidence of cerebral ischemia as indicated by post-operative neurological exam
- Evidence of injury to artery as seen on post-operative imaging of the carotid artery either by carotid duplex ultrasound or angiogram

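### Both primary components are recorded in two places under different rules, and neither document says which items give the primary incidence

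*Protocol*

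**What the plan says.** Protocol 2.2 defines the endpoint: "The primary endpoint of this study is evidence of injury to the artery or cerebral ischemia secondary to shunt placement and removal". It gives no time window. Protocol 6 and SAP 7.1 describe the analysis in one sentence, which leaves out removal: "The primary objective will be evaluated by summarizing the incidence of injury to the artery or cerebral ischemia secondary to shunt placement". Neither section names a CRF item.

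The two components are then collected twice.

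- **Post-operative assessment** (Protocol 5, SAP 7.2.6). The heading is "Post-operative Assessment (up to 60 days post-procedure"). The items are "Evidence of cerebral ischemia as indicated by post-operative neurological exam" and "Evidence of injury to artery as seen on post-operative imaging of the carotid artery either by carotid duplex ultrasound or angiogram". Neither asks whether the shunt was the cause.
- **Device performance** (Protocol 5.1, SAP 7.2.7). Question 10 asks "Was there evidence of post-operative cerebral ischemia noted in the neurological exam". Question 11 asks "Did the subject experience injury to the artery due to the device as evidenced by the imaging of the carotid artery", by duplex or angiogram. Neither states a window.

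Protocol 5.1 adds that a medical record silent on a yes/no question is taken as a no. SAP 7.3 plans no imputation and bases summaries on non-missing data. Inclusion criterion 3 requires "Availability of records on post-operative imaging" of the carotid, with no limit on when the scan was done. Questions 5 and 9 also ask about arterial damage, at insertion and at removal of the shunt.

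**The concern.** The study has no comparator and no hypothesis test, so its one primary result is an incidence. That figure means only what its numerator, window and denominator make it mean, and the plan fixes none of the three.

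Three things are at stake. First, subjects are numbered backwards in time from study initiation, so time since surgery differs between them. An item without a window therefore observes them for unequal periods. Second, a subject without a neurological exam or a scan inside 60 days can count as event-free in one source and be missing in the other. Third, SAP 7.2.6 and 7.2.7 produce both tables, and nothing prevents the headline rate from being chosen after both have been seen.

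**Working it through.** There is no planned figure to reproduce: the documents give no expected rate, and 100 is a fixed count. The check is a comparison of the text, followed by an illustration with assumed counts.

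**1. The two collections side by side**

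| | Post-operative assessment | Questions 10 and 11 |
|---|---|---|
| Window | 60 days (heading) | none stated |
| Attribution, ischemia | none | none (question 10) |
| Attribution, arterial injury | none | to the device (question 11) |
| Silent record | no rule; if left missing, dropped under SAP 7.3 | entered as no (Protocol 5.1) |

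For ischemia, the sources differ in window and in the silent-record rule. For arterial injury, they differ in attribution as well. No ischemia item in either set captures the link to the shunt that the endpoint requires.

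**2. Eligibility against the window**

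A subject whose only scan was at 12 months meets criterion 3 and can be answered on question 11, but has no imaging within 60 days. For ischemia, no inclusion criterion requires a recorded neurological exam. A subject without one becomes a no on question 10 and has nothing to enter in the assessment.

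**3. Effect of the silent-record rule on one component**

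Assume x = 5 events, N = 100 subjects and m silent records, none of them among the events. If silence means no, the rate is x/N. On non-missing data it is x/(N − m). Intervals are exact (Clopper-Pearson) 95%.

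| m | Silence = no | Non-missing data |
|---|---|---|
| 0 | 5/100 = 5.0% (1.6 to 11.3) | 5/100 = 5.0% (1.6 to 11.3) |
| 10 | 5/100 = 5.0% | 5/90 = 5.6% (1.8 to 12.5) |
| 20 | 5/100 = 5.0% | 5/80 = 6.3% (2.1 to 14.0) |
| 30 | 5/100 = 5.0% | 5/70 = 7.1% (2.4 to 15.9) |

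**4. Effect of attribution (arterial injury only)**

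Assume 5 of 100 subjects have injury on imaging within 60 days. The assessment gives 5.0%. If 5, 3 or 1 of these are judged due to the device, question 11 gives 5.0%, 3.0% (0.6 to 8.5) or 1.0% (0.03 to 5.45).

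**5. Zero events**

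The exact upper 95% limit is 1 − 0.025^(1/n). For n = 100 it is 3.6%. If 20 subjects were imaged only after day 60, n = 80 and it is 4.5%.

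**The case against.** The strongest reply is that the plan has a single endpoint with attribution built in, so the unattributed assessment items are not a rival primary rate. Protocol 5.1 also sits inside section 5, whose only post-operative window is 60 days, and questions 10 and 11 refer to the exam and the imaging as if to the same review. SAP 7.3 already removes subjects without data from the assessment items. Both sets are summarized and assessment details are listed by subject, so disagreement should be visible.

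Part of this stands. A reader might infer that the study necessarily holds two different primary rates. The documents do not support that: the two sets may agree, as the first row of the table in step 3 shows. A reader might also infer that device attribution applies to both questions, but question 10 has none. Nor does the text support a general claim that unrelated late injuries will inflate question 11, because its wording leaves only injuries judged due to the device. Late unrelated findings are a more natural worry for question 10.

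The rest does not answer the point. No text extends the 60-day limit to questions 10 and 11. The attribution argument cannot select a source for ischemia, since neither item has attribution. SAP 7.3 has nothing to act on once a silent record has been entered as no. Listings make disagreement visible but do not say which rate is primary.

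**Conclusion.** The point holds as a gap in the definition of the primary result. The same two components are collected under non-identical rules, eligibility admits subjects with no imaging inside the plan's own window, and no rule names source, denominator or precedence. The same charts can therefore give different primary incidences, though they need not.

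The size cannot be known from the documents. Under the assumed counts, the silent-record rule alone moves a 5.0% rate to anything up to 7.1%, and attribution moves a 5.0% injury rate to anything down to 1.0%. These shifts are small beside the confidence intervals. They are systematic, however, and can be removed by wording. The gap should be closed before the data are summarized.

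**What to change.** 1. Apply the existing 60-day window to questions 10 and 11. Record each component once, with a separate field for attribution to shunt placement or removal, for ischemia as well as injury.
2. In SAP 7.1, define the primary incidence as shunt-attributed arterial injury (on imaging within 60 days, or intraoperatively in questions 5 and 9) or shunt-attributed ischemia within 60 days. Report the unattributed rate beside it. Using the unattributed items alone would change the endpoint.
3. For the imaging and exam components, use as denominator the subjects actually imaged or examined within 60 days, and do not read a silent record as no for these two items. State how a subject evaluable on only one component is counted in the composite.
4. Choose one route for late imaging. Either add the 60-day limit to criterion 3, which makes late-imaged subjects ineligible, or leave eligibility as it is and report them as non-evaluable for the imaging component. Doing both would be redundant.

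The cost is a short amendment to the protocol, CRF and SAP. Questions 10 and 11 and criterion 3 are protocol text, so changing the SAP alone is not enough, and the first route under item 4 changes eligibility. The imaging and exam denominators may be somewhat smaller and the intervals slightly wider.

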1.2 Study Device

1.2.1 Device Description

The Integra Sundt™ internal and external (Loop) Carotid Endarterectomy Shunts are designed to provide temporary carotid bypass for cerebral circulation during carotid endarterectomy procedures.

The Sundt™ internal and external Carotid Endarterectomy shunts are constructed of silicone elastomer with stainless steel spring reinforcement to minimize kinking and occlusion of the cannula lumen and to aid in the ease of insertion of the proximal and distal ends. The ends of the shunts have cone-shaped bulbs to facilitate fixation of the shunt in the vessel. Quite frequently in the internal type shunt a distal tourniquet is not required because, if the proper shunt size is selected, the bulb fits firmly enough against the wall of the vessel that there is no bleeding around the distal bulb. A tourniquet is always required on the proximal end of both the external and internal shunts and usually on the distal end of the external shunt

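### A post-operative scan that cannot show whether the shunt injured the artery would be counted as no injury, because question 11 has no not-evaluable answer

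*Protocol*

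**What the plan says.** Arterial injury is one of the two halves of the primary endpoint (Protocol 2.2, SAP 3.1), and the primary objective is evaluated by summarising the incidence (Protocol 6, SAP 7.1).

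The imaging evidence enters in three places:

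- Eligibility, Protocol 4.1 criterion 3: "Availability of records on post-operative imaging of the carotid artery either by carotid duplex ultrasound or angiogram".
- The post-operative item, SAP 7.2.6, matching Protocol 5: "Evidence of injury to artery as seen on post-operative imaging of the carotid artery either by carotid duplex ultrasound or angiogram". The window in the item's title, "Post-operative Assessment (up to 60 days post-procedure"), limits time and not anatomy.
- Question 11, Protocol 5.1 and SAP 7.2.7: "Did the subject experience injury to the artery due to the device as evidenced by the imaging of the carotid artery either by carotid duplex" (an angiogram also qualifies).

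None of these names the part of the artery to be shown, sets a minimum quality, or provides for a scan that cannot answer the question. Modality is not among the listed data items.

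For the yes/no questions, Protocol 5.1 adds that "if the medical record is silent on the answer to the question it will be assumed that the answer is" no. SAP 7.2.2 bases every analysis on the safety population, defined only by having had the operation with this shunt. SAP 7.3 plans no imputation and summarises non-missing data.

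On where the shunt meets the vessel, Protocol 1.2.1 says: "The ends of the shunts have cone-shaped bulbs to facilitate fixation of the shunt in the vessel". It also says: "A tourniquet is always required on the proximal end of both the external and internal shunts".

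**The concern.** A scan shows that the artery was not injured only if it could have shown an injury. The plan treats every eligible scan as able to do so. Informative negatives and uninformative scans get the same answer, enter the same denominator, and are not separated in any planned summary.

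The study is descriptive, with no comparator and no hypothesis, so the reported incidence is its main result. If some negatives carry no information, a low imaging-detected injury rate partly reflects what the scans and their reports covered.

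**Working it through.** **1. How each kind of scan is scored.**

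| Post-operative scan | What the plan does | Answer to question 11 | In the denominator |
|---|---|---|---|
| Report addresses the shunted part, no injury | Answered from the report | no | yes |
| Report does not address the shunted part | Silent-record rule, Protocol 5.1 | no | yes |
| Report says non-diagnostic | Only yes or no on offer, and no injury was shown | no | yes |

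Only the first row is evidence of no injury. SAP 7.3 does not remove the other two, because an entered no is not a missing value and no rule sets such a scan to missing. The SAP does not repeat the silent-record rule, so the two documents also need to be reconciled on this question.

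**2. The plan's own figure.** The sample size of 100 (Protocol 3.2, SAP 6) comes with no expected rate or precision target. There is nothing to reproduce, and this point does not dispute it.

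**3. Direction.** Let p be the true imaging-detectable injury rate and c the share of informative scans. Neither is in the documents, so both are assumed, with c taken as unrelated to injury. Scoring the rest as no over all 100 gives

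reported rate = c × p, which is at most p.

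With p = 5%:
- c = 0.90: 4.5%
- c = 0.75: 3.75%
- c = 0.50: 2.5%
- c = 0.25: 1.25%

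If c = 1 there is no bias.

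**4. If no injury is seen.** The exact two-sided 95% upper limit with 0 events in n informative scans is 1 − 0.025^(1/n).

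| Informative scans n | Upper limit |
|---|---|
| 100 | 3.6% |
| 90 | 4.0% |
| 75 | 4.8% |
| 50 | 7.1% |
| 25 | 13.7% |

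**5. Chance of seeing at least one injury**, 1 − (1 − p)^n:
- p = 5%: 99.4% with n = 100, 92.3% with n = 50, 72.3% with n = 25.
- p = 2%: 86.7%, 63.6% and 39.7%.

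**6. Checking the repair.** Assume p = 5%, 50 full scans, and 50 partial scans that detect half of the injuries. Full scans show 50 × 0.05 = 2.5 injuries and 47.5 clean results. Partial scans show 50 × 0.05 × 0.5 = 1.25 injuries.
- All subjects: (2.5 + 1.25)/100 = 3.75%, too low.
- Evaluable scans, same rule for positives and negatives: 2.5/50 = 5.0%, correct.
- Partial-scan positives kept but partial-scan negatives dropped: 3.75/(3.75 + 47.5) = 7.3%, too high.

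The evaluable-scan rate is therefore sound only if numerator and denominator follow one rule.

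**The case against.** **No passage shows that any scan is uninformative.** A reader might infer that eligible scans do miss the shunt ends, or that duplex covers less than angiography so that the mix of modalities moves the result. The documents say neither. This stands: the direction follows from the scoring rules, but the frequency is unknown, and modality should be tabulated because it is unrecorded, not because a difference is established.

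**The device description does not say where injury occurs.** A reader might infer that injury must be sought at a bulb and a tourniquet at each end. Protocol 1.2.1 puts a bulb at each end, but a tourniquet in every case only proximally; a distal one is often unnecessary with the internal type. The endpoint is injury to the artery, not injury at those sites. This stands, and the point needs only that a report may not address the part the shunt occupied.

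**Injury has other routes into the data.** Questions 5, 9 and 12 and the operative-report complications do not depend on imaging, and ischemia is the other half of the endpoint. This limits the effect to the imaging component. It does not remove it: questions 5, 9 and 12 fall under the same silent-record rule, and the documents do not say how they combine with question 11.

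**Something might show up anyway.** SAP 7.2.6 promises by-subject listings and Protocol 10 raw data listings, and the full case report form is not among the documents. It would be too strong to say that the problem must stay hidden. But neither document requires modality or evaluability to be recorded, so the listings need not show them.

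**The shift may be small.** With p = 5% and 90% informative scans it is half a patient per 100, well inside the exact 95% interval of 1.6% to 11.3% for 5/100. This is fair as to that case. Sampling error is visible to the reader, however, whereas a negative that carries no information is not.

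**Conclusion.** The point holds for the imaging component of the primary incidence. Under the plan's rules a scan that cannot answer question 11 is counted as no injury, SAP 7.3 does not undo this, and the error can only lower the reported rate.

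Its size cannot be derived from the documents. Every rate in the illustration is assumed, and the bias is zero if all scans are informative. The most useful gauge is the case of no injuries seen: an upper limit of 3.6% if all 100 scans count as evidence, against 7.1% if 50 do. The evaluable-scan rate also assumes that evaluability is unrelated to injury.

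A reader might infer that the study's injury rate will be materially understated. The documents do not support that. They support the narrower statement that the plan does not require the information needed to tell. This makes it a modest improvement worth making because it is cheap.

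**What to change.** **Protocol 5 and 5.1 (and SAP 7.2.7).** Record the imaging modality. Give question 11 three answers: yes, no, and not evaluable. Not evaluable means non-diagnostic, or the shunted segment stated as not seen or not addressed in the report. Exempt question 11 from the silent-record rule.

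**SAP 7.1 and 7.2.6.** Report:
- imaging-detected injury over all subjects, as the lower figure;
- the number not evaluable;
- the rate among evaluable scans, with evaluability judged by the same rule for positive and negative scans;
- all of these by modality.

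List injuries seen on otherwise non-evaluable scans separately, and count them in the all-subject figure only. Keep every subject in the analyses of ischemia and of operative injury (questions 5 and 9).

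**Cost.** One new field and one changed answer set, completed from reports already under review, plus a short SAP addition and one table. No new imaging or patients are needed. The imaging denominator becomes smaller and the rate may be less favourable. Where reports do not describe what was seen, the not-evaluable group could be large, and its size would then be a result worth reporting.

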6 STATISTICAL ANALYSIS

The PMCF is a retrospective chart review. All analyses will be descriptive in nature. No formal statistical analyses will be performed. The study objectives will be presented by summary statistics.

Summary statistics (mean, standard deviation, quintiles, counts, and percentages) will be presented for all demographic (i.e. age, gender, etc.), clinical baseline characteristics (diagnosis, medical history, medications), surgical procedures (procedures performed, duration of surgery) and complications.

The primary objective will be evaluated by summarizing the incidence of injury to the artery or cerebral ischemia secondary to shunt placement.

All statistical analysis will be conducted using SAS.

